**Table 2: Visit Schedule for Interventional Part-Extension Phase**

Schedule of Events	Interventional Part-Extension Phase													Follow-Up	
														EOT	EOS
Weeks	13	14	15	17	19	21	23	25	27	29	31	33	35	37	45
Visits window allowed (Day)	±1	±1	±1	±2	±2	±2	±2	±2	±2	±2	±2	±2	±2	±2	±3
Body weight	X			X		X		X		X		X		X	X
Adverse Events (1)	X	X	X	X	X	X	X	X	X	X	X	X	X	X	X
Concomitant Medications (1)	X	X	X	X	X	X	X	X	X	X	X	X	X	X	X
Vital Signs (1)	X	X	X	X	X	X	X	X	X	X	X	X	X	X	X
Physical Exam (2)	X		X	X	X	X	X	X	X	X	X	X	X	X	X
Safety Laboratory Tests, Including Urinalysis (3)	X					X				X				X	X
ECG (4)	X													X	X
Serum Pregnancy Test															
Urine Pregnancy Test (5)	X			X		X		X		X		X		X	
Clinical Evaluations (IASI, IGA, and PRO) (2)	X		X	X	X	X	X	X	X	X	X	X	X	X	
Skin Photography (2)	X		X	X	X	X	X	X	X	X	X	X	X	X	
Mechanistic Evaluations (PD biomarkers) - TEWL (6)	X							X						X	
Mechanistic Evaluations (PD biomarkers) - Skin Tape Harvests (6)	X							X						X	
Mechanistic Evaluations (PD biomarkers) - Blood (7)	X					X		X		X				X	
Randomization															
Dose Administration (8)	X	X	X	X	X	X	X	X	X	X	X	X	X		
PK (blood) (9)	X		X	X	X	X	X	X	X	X	X	X	X	X	X
PK (skin) (10)	X														
ADA (blood) (11)	X			X		X		X		X		X		X	X

Abbreviations: ADA = Anti-drug Antibody, ECG = Electrocardiogram, EOS = End of Study, EOT = End of Treatment, IASI = Ichthyosis Area Severity Index, IGA = Investigator Global Assessment, IP = Interventional Part, IV = intravenous, OP = Observational Part, PD = Pharmacodynamics, PK = Pharmacokinetics, PRO = Patient-Reported Outcome, SC = subcutaneous, TEWL = Transepidermal water loss.

\*Screening will occur during the 28 days preceding Week 1 of OP; ^Baseline is pretreatment on Day 1 of Week 1 of Interventional Part Main Phase

(1) To be recorded at Screening; at Weeks 1, 5, and 9 during OP; every other week during IP before dose administration; and at Weeks 37 EOT and 45 EOS.

- (2) To be performed at Screening; at Weeks 1, 5, and 9 during OP; every other week (ie, at odd-numbered weeks, to start with Week 1) during IP before dose administration; and at Week 37 EOT and 45 EOS (except clinical evaluations [IASI, IGA, and PRO] and skin photography, which will not be performed at Week 45 EOS).
- (3) To be performed at Screening; at Week 1 during OP; at Weeks 1, 5, 9, 13, 21, and 29, during IP before dose administrations; and at Weeks 37 EOT and 45 EOS.
- (4) To be performed at Screening; at Weeks 1, 5, 9, and 13 during IP before dose administration; and at Weeks 37 EOT and 45 EOS.
- (5) To be performed at Weeks 1, 5, 9, 13, 17, 21, 25, 29, and 33 during IP before dose administrations; and at Week 37 EOT.
- (6) To be performed at Week 1 during OP and at Weeks 1, 13, and 25 during IP before dose administration; and at Week 37 EOT. Skin tape harvests will allow assessing the skin concentrations of mediators of skin inflammation and homeostasis and skin KLK5 activity.
- (7) To be performed at Weeks 1, 5, and 9 during OP; at Weeks 1, 5, 9, 13, 21, 25, and 29 during IP before dose administration; and at Week 37 EOT.
- (8) To be given at Weeks 13, 14, and 15 and every other week during IP-Extension Phase. Dose administration will be SC.
- (9) To be collected every other week (ie, at odd-numbered weeks, to start with Week 1) during IP before dose administration; and at Weeks 37 EOT and 45 EOS. Blood samples will be collected no more than 1 hour before the start of dose administration.
- (10) Optional skin biopsy will be a 3-mm biopsy to be collected before dose administration at Week 13 to assess epidermis-to-dermis DS-2325a concentration ratio.
- (11) To be collected at Weeks 1, 5, 9, 13, 17, 21, 25, 29, and 33 during IP before dose administration; and at Weeks 37 EOT and 45 EOS.

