- (2) To be performed at Screening; at Weeks 1, 5, and 9 during OP; every other week (ie, at odd-numbered weeks, to start with Week 1) during IP before dose administration; and at Weeks 37 EOT and 45 EOS (except clinical evaluations [IASI, IGA, and PRO] and skin photography, which will not be performed at Week 45 EOS).
- (3) To be performed at Screening; at Week 1 during OP; at Weeks 1, 5, 9, 13, 21, and 29, during IP before dose administration; and at Weeks 37 EOT and 45 EOS.
- (4) To be performed at Screening; at Weeks 1, 5, 9, and 13 during IP before dose administration; and at Weeks 37 EOT and 45 EOS.
- (5) To be performed at Weeks 1, 5, 9, 13, 17, 21, 25, 29, and 33 during IP before dose administrations; and at Week 37 EOT.
- (6) To be performed at Week 1 during OP and at Weeks 1, 13, and 25 during IP before dose administration; and at Week 37 EOT. Skin tape harvests will allow assessing the skin concentrations of mediators of skin inflammation and homeostasis and skin KKL5 activity.
- (7) To be performed at Weeks 1, 5, and 9 during OP; at Weeks 1, 5, 9, 13, 21, 25, and 29 during IP before dose administration; and at Week 37 EOT.
- (8) To be given at Weeks 1, 2, and 3 and every other week during IP-Main Phase. Dose administration will be IV at Week 1 and then SC.
- (9) To be collected every other week (ie, at odd-numbered weeks, to start with Week 1) during IP before dose administration; and at Weeks 37 EOT and 45 EOS. Blood samples will be collected no more than 1 hour before the start of dose administration.
- (10) On Week 1 of IP, PK blood sample will also be collected at the end of infusion (ie, 1 hour after start of dose administration) and 1 hour later (ie, 2 hours after start of dose administration). These two blood samples will be collected  $\pm$  10 minutes from the nominal times.
- (11) To be collected at Weeks 1, 5, 9, 13, 17, 21, 25, 29, and 33 during IP before dose administration; and at Weeks 37 EOT and 45 EOS.

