### **3. STUDY DESIGN**

#### **3.1. Overall Design**

##### **3.1.1. Overview**

This Phase 1b/2 study will enroll a total of 9 to 12 patients with NS and will be conducted entirely at 1 site in France, an NS center of excellence and referral which is expected to enroll NS patients with well-known disease histories at a relatively high rate.

It will be articulated in an Observational Part (12 weeks), during which patients will not be treated and will be investigated only to understand the course of their disease, an Interventional Part, during which patients will be treated with DS-2325a to understand its properties as a candidate drug product, and a Follow-Up, during which safety will be monitored after treatment.

The Interventional Part will be further articulated into 2 phases: A Main Phase (12 weeks) and an Extension Phase (24 weeks). The Interventional Part Main Phase is the core component of the study. It will be immediately and seamlessly preceded by the Observational Part and will be followed, also immediately and seamlessly, by the Interventional Part Extension Phase, as long as at the end of the Main Phase ECS is found as initial evidence of efficacy and warrants study continuation. All patients will transition from the Main Phase to the Extension Phase; however, the latter will be discontinued if ECS is not found. The Interventional Part Main Phase will be double-blinded and placebo-controlled: Patients will be randomized to 2 parallel arms to receive DS-2325a or placebo in a 2:1 ratio and will receive DS-2325a or placebo SC every other week, except for the initial (“loading”) dose, which will be administered by an IV infusion. The Extension Phase will be open-label and all patients will receive DS-2325a SC every other week. However, during both Main Phase and Extension Phase, a 600 mg SC dose will also be given one week after the first dose of the phase, coinciding with one week before following biweekly doses. Thus, eDS-2325a will be given at Weeks 1, 2, 3, 5, 7, 9, etc. Intravenous dose will not be given in Interventional Part Extension Phase. In case of patient(s) showing benefit from treatment with DS-2325a, the protocol of this study will be amended to allow a prolongation of the Extension Phase and, therefore, a continuation of DS-2325a administration within the clinical trial framework beyond the currently foreseen end. This should ensure that benefiting patient(s) will continue receiving cure.

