### **3.3. Stopping Rules**

#### **3.3.1. Subject-level Safety Stopping Rules**

For any subject experiencing the following events, treatment will be suspended until further evaluation by the Data Monitoring Committee (DMC).

- Any event severe in nature (eg, severe injection site reaction, severe allergic reaction, etc) deemed by the DMC as necessitating further safety review before treatment can be continued
- Hy's Law event: Alanine aminotransferase [ALT] or aspartate aminotransferase [AST]  $\geq 3 \times$  upper limit of normal [ULN] with simultaneous total bilirubin  $\geq 2 \times$  ULN)
- QTc prolongation: QT interval corrected with Fridericia's formula (QTcF)  $> 500$  msec OR increase in QTcF from pre-dose baseline of  $> 60$  msec

After an in-depth review of subject-level data is conducted by the DMC, one of the following recommendations will be made:

- To continue with treatment as planned
- To continue treatment, but at a reduced dose
- To terminate participation in the study

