#### **3.3.2. Population-level Safety Stopping Rules**

The DMC, as part of continuous monitoring of safety, will evaluate the data across the study for the following criteria:

- One active-treated subject experiences an AE of severe intensity (eg, severe injection site reaction, severe allergic reaction, etc) that is related to the study drug OR two active-treated subjects experience the same AE of moderate intensity that is related to the study drug.
- One active-treated subject with ALT or AST  $>5 \times$  ULN or serum total bilirubin  $>2 \times$  ULN.

If any of the above criteria are met, an in-depth review of data will be conducted by the DMC, and one of the following recommendations will be made:

- To continue with the study as planned, with no change
- To continue with the study as planned, with modification to the safety monitoring plan
- To continue with the study, but at a reduced dose
- To terminate the study

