### **16.2. Blood Collection Volume by Category and Total**

The details are available in the ICF.

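### Placebo patients switching to DS-2325a at Week 13 have no scheduled safety laboratory test for their first 8 weeks on drug; add one at Week 17

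*Combined protocol and SAP*

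**What the plan says.** Section 3.1.1 states: "The Extension Phase will be open-label and all patients will receive DS-2325a SC every other week". There is no IV loading dose in this phase, and each dose is 600 mg. Table 2, footnote (8), sets the dosing weeks: "To be given at Weeks 13, 14, and 15 and every other week during IP-Extension Phase".

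Safety laboratory tests are tied to study week. Table 2, footnote (3), schedules them "at Weeks 1, 5, 9, 13, 21, and 29, during IP before dose administrations", then at Weeks 37 and 45. Table 1 gives the same list: "at Week 1 during OP; at Weeks 1, 5, 9, 13, 21, and 29, during IP before dose administration". Tables 3 and 4 in Section 16.3 repeat it, and the laboratory rows of the tables agree with the footnotes. Section 6.2.4 refers to Section 16.3 for Extension Phase procedures and gives no separate schedule for patients coming from placebo.

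Two rules depend on laboratory results:

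- The subject-level hold (Sections 3.3.1 and 5.8) applies when ALT or AST is at least 3 × ULN with simultaneous total bilirubin of at least 2 × ULN.
- The population-level review (Section 3.3.2) begins "One active-treated subject with ALT or AST" and sets the limits at above 5 × ULN for ALT or AST, or above 2 × ULN for total bilirubin.

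**The concern.** For a placebo patient, Week 13 is the first day of exposure. The protocol partly treats it as a fresh start: the extra dose one week after the first is repeated, and the tight ±1-day windows return at Weeks 13, 14 and 15. The laboratory schedule does not restart. The 4-week check used for first exposure in the Main Phase is therefore missing for the patients first exposed in the Extension Phase.

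Safety is the primary objective and endpoint, and Section 1.5 counts laboratory findings among the practices that protect patients. A rise in ALT, AST or bilirubin without symptoms is found only by a blood test. If the first scheduled test falls at 8 weeks, the hepatic rules have no scheduled data to act on before then, and dosing continues in the meantime.

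**Working it through.** The sample size has no power basis (Section 10.5), so there is no plan figure to reproduce. The check is a count from the schedule.

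**Inputs**

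- Main Phase dosing: Weeks 1, 2, 3, 5, 7, 9, 11 (Table 1, footnote 8). Week 1 is 1000 mg IV; the rest are 600 mg SC.
- Extension Phase dosing: Weeks 13, 14, 15, 17, 19, 21 and every other week to Week 35, 600 mg SC each (Table 2).
- Safety laboratory tests: Weeks 1, 5, 9, 13, 21 and 29, pre-dose (footnote 3).
- Visit windows: ±1 day at Weeks 1 and 13; ±2 days at Weeks 5, 17 and 21.
- Allocation 2:1, 9 to 12 patients (Sections 5.3 and 10.5).

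**Patients affected:** 9/3 = 3, or 12/3 = 4.

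**Time from first active dose to first scheduled on-drug test**

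- Switching patients: (21 − 13) × 7 = 56 days. Windows add 1 + 2 = 3 days either way, giving 53 to 59.
- DS-2325a arm: (5 − 1) × 7 = 28 days, giving 25 to 31.

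**Doses and cumulative amount before each test** (tests are pre-dose, so that day's dose is excluded)

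| Group and test | Time on drug | Doses given at Weeks | Number | Cumulative dose |
|---|---|---|---|---|
| DS-2325a arm, Week 5 | 4 weeks | 1, 2, 3 | 3 | 1000 + 2 × 600 = 2200 mg |
| DS-2325a arm, Week 9 | 8 weeks | 1, 2, 3, 5, 7 | 5 | 1000 + 4 × 600 = 3400 mg |
| Switching, Week 17 (not scheduled) | 4 weeks | 13, 14, 15 | 3 | 3 × 600 = 1800 mg |
| Switching, Week 21 | 8 weeks | 13, 14, 15, 17, 19 | 5 | 5 × 600 = 3000 mg |

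**Effect of adding Week 17:** the first on-drug test moves from 56 to 28 days (25 to 31 with windows) and from 5 doses to 3. That is 4 weeks and 2 doses (3000 − 1800 = 1200 mg) earlier. Switching patients then have the same 4-week/3-dose and 8-week/5-dose tests as the DS-2325a arm.

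**Is blood already drawn at Week 17?** Yes. ADA sampling is "To be collected at Weeks 1, 5, 9, 13, 17, 21, 25, 29, and 33 during IP before dose administration", and a PK sample is marked at the same visit.

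**The case against.** The strongest case is that this is a choice of interval and not an error. The tables and text agree with each other, and the only benchmark is the Main Phase, where patients receive a 1000 mg IV dose first. At matched times switching patients have received 400 mg less (1800 against 2200 mg; 3000 against 3400 mg). Section 1.2 reports no toxicologically significant animal findings, and Section 8.3 identifies no potential risks. Section 1.4 reports only mild adverse events in healthy subjects, including those given 600 mg weekly four times (2400 mg). The 6 to 8 patients on DS-2325a are tested at Weeks 5, 9 and 13. Between Weeks 13 and 21, adverse events and vital signs are checked at every visit and physical examination is done at Weeks 15, 17 and 19. The severe-event hold applies, and the DMC reviews safety data and can recommend changes to monitoring. Redacted text, the IB or the DMC charter might explain the interval.

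Most of this stands, and it limits the weight of the point. It does not close the gap. None of the continuing checks yields an ALT, AST or bilirubin value, an unscheduled test needs a prompt, and the DMC can review only what is collected. The Phase 1a data are preliminary and blinded, and the repeat-dose experience in Section 1.4 is four doses; a switching patient has had five before the first scheduled test.

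Two further objections are fair but do not change the conclusion. A pre-dose Week 17 result may return after that day's dose, but the same delay applies at Week 21, so the gain of 2 doses is unchanged. The ECG schedule has a longer gap of the same kind, from Week 13 pre-dose to Week 37, which a Week 17 laboratory test does not address.

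**Conclusion.** The concern holds. In 3 of 9 or 4 of 12 patients, the first scheduled on-drug safety laboratory test comes 56 days and 5 doses after first exposure, against 28 days and 3 doses in the DS-2325a arm. No scheduled test can trigger the hepatic hold or review in these patients before Week 21; an unscheduled test still can.

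The count assumes exact 2:1 allocation, no placebo patient lost before Week 13, doses and visits on schedule, and an Extension Phase that is still running at Week 21. That 8 weeks is too long is a judgement, resting on the protocol's own 4-week check for first exposure in the Main Phase. With no identified liver signal and a lower cumulative dose, this is a change that should be made because it improves patient safety at little cost; it does not undermine the trial.

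**What to change.** Add the safety laboratory tests, including urinalysis, pre-dose at Week 17 for all patients. Mark Week 17 in the laboratory row of Tables 2 and 4, and change the Interventional Part list in footnote (3) of Tables 1 to 4 to Weeks 1, 5, 9, 13, 17, 21 and 29. Draw the tubes with the PK and ADA samples. Testing everyone, rather than only switching patients, keeps the schedule from revealing Main Phase allocation. A Week 25 test is optional, and would serve only to match the DS-2325a arm's 12-week test.

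The cost is one extra set of routine tubes and one urinalysis per patient, plus a schedule amendment. No visit or venipuncture is added. Section 16.2 says of blood volumes: "The details are available in the ICF". The consent form may therefore need an updated volume with ethics approval; the size of that change cannot be checked from the protocol.

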## LIST OF ABBREVIATIONS

ABBREVIATION	DEFINITION
ADA	Anti-drug antibodies
AE	Adverse Event
ALP	Serum alkaline phosphatase
ALT	Serum alanine aminotransferase
AST	Serum aspartate aminotransferase
AUC	Area Under the Plasma Concentration-time Curve
AUC t	Area Under the Plasma Concentration-time Curve up to time
AUC t,ss	Area Under the Plasma Concentration-time Curve up to time t at steady state
BMI	Body Mass Index
BSA	Body Surface Area
CCL20	Chemokine-C-C motif ligand 20
CFR	Code of Federal Regulations
CK	Creatine Kinase
CL	total body clearance
CL/F	Apparent Total Body Clearance
C max	Maximum Plasma Concentration
COVID-19	Coronavirus disease 2019
CRO	Contract Research Organization
CTCAE	Common Terminology Criteria for Adverse Events
C trough	trough concentration
CV%	Coefficient of variation percentage
DLQI	Dermatology-Life-Quality-Index
DMC	Data Monitoring Committee
EC	Ethics Committee
ECG	Electrocardiogram
eCRF	Electronic Case Report Form
ECS	Early clinical signal
EDC	Electronic Data Capture
EOS	End of Study
EOT	End of Treatment

ABBREVIATION	DEFINITION
EU	European Union
FDA	Food and Drug Administration
GCP	Good Clinical Practice
GGT	$\gamma$ -Glutamyl Transferase
HBV	Hepatitis B Virus
HCV	Hepatitis C Virus
HIV	Human Immunodeficiency Virus
HS	healthy subjects
IASI	Ichthyosis Area Severity Index
IB	Investigator's Brochure
IC 50	half-maximal inhibition
ICF	Informed Consent Form
ICH	International Council for Harmonisation
Ig	Immunoglobulin
IGA	Investigator Global Assessment
IL	Interleukin
ILC	Ichthyosis linearis circumflexa
INN	International Non-proprietary Name
IRB	Institutional Review Board
ISRs	Injection Site Reactions
IV	intravenous
ITT	Intent-to-Treat
IXRS	Interactive Web/Voice Response System
KLK	Kallikrein-Related Peptidase
K ed	epidermis-to-dermis DS-2325a concentration ratio
LDH	Lactate Dehydrogenase
LEKTI	lympho-epithelial Kazal-type-related inhibitor
MAD	multiple ascending dose
MedDRA	Medical Dictionary for Regulatory Activities
mITT	Modified Intent-to-Treat
NOAEL	no observed adverse effect level
NRS	Numerical Rating Scale

ABBREVIATION	DEFINITION
NS	Netherton Syndrome
NS-ILC	Netherton Syndrome -ichthyosis linearis circumflexa
NS-SE	Netherton Syndrome-scaly erythroderma
PAR2	protease-activated receptor 2
PD	Pharmacodynamic
PK	Pharmacokinetic
PRO	Patient-reported outcome
RNA	Ribonucleic Acid
SAD	single ascending dose
SAE	Serious Adverse Event
SAP	Statistical Analysis Plan
SC	subcutaneous
SD	Standard deviation
SOP	Standard Operating Procedure
SAVER	Serious Adverse Event Report
SPINK	serine peptidase inhibitor Kazal type
SPINK5	serine peptidase inhibitor of Kazal type 5
SUSAR	Suspected Unexpected Serious Adverse Reaction
TARC	thymus and activation-regulated chemokine
TBL	Total bilirubin level
TEAE	Treatment-emergent Adverse Event
TEWL	Transepidermal water loss
TNF	Tumor necrosis factor
TSLP	thymic stromal lymphopoietin
ULN	upper limit of normal

## 1. INTRODUCTION

### 1.1. Background

Netherton Syndrome (NS) is a severe rare disease caused by autosomal recessive mutations in the serine peptidase inhibitor of Kazal type 5 (SPINK5) gene on chromosome 5q32. It is part of a group of genetically determined skin diseases referred to as ichthyoses, which are characterized by generalized scaling, erythema, and epidermal barrier defects and also include congenital ichthyosiform erythroderma, lamellar ichthyosis, and epidermolytic ichthyosis. The SPINK5 gene encodes lympho-epithelial Kazal-type-related inhibitor (LEKTI), which plays a critical role in maintaining skin barrier function and regulating desquamation of keratinocytes by inhibiting Kallikrein-Related Peptidase 5 (KLK5). Since SPINK5 mutations result in loss of functional LEKTI, KLK5 is excessively activated in the skin of NS patients.

Although the prevalence of NS is not well documented, there is a reported worldwide birth incidence of 1 in 200,000. The estimated number of patients in the United States is around 2,000 and in the European Union more than 2,000. Clinically, NS main features include congenital ichthyosiform erythroderma, a hair shaft abnormality known as trichorrhexis invaginata (bamboo hair), and severe atopy. However, NS phenotype is variable. Two main presentations are recognized: NS-ichthyosis linearis circumflexa (NS-ILC) and NS-scaly erythroderma (NS-SE). Aside from the appearance of the skin, pruritus is a constant feature and a substantial quality-of-life issue. The first manifestation of NS is typically in the neonatal period, where erythroderma and sparse hair are present. Netherton Syndrome can be life-threatening in neonates, in whom the compromised skin barrier leads to severe dehydration, hypothermia, weight loss, and sepsis. Failure to thrive is common in infancy as a result of chronic fluid loss, persistent cutaneous infections, and malnutrition. Mortality rate has been reported in infancy from 30% to 40%. Most patients survive the neonatal period, however, and show improvement of their symptoms over time, but NS remains a serious and debilitating condition with relentless negative impact also throughout adulthood. Patients continue showing generalized erythroderma and suffering from pruritus and are additionally afflicted by atopic disorders such as food allergies and asthma. Netherton Syndrome often takes a relapsing and remitting course, characterized by flares of intermittent redness and patches of ichthyosis linearis circumflexa (ILC), which may occur every 1 to 2 months, apparently precipitated at times by stress or infection. The etiopathogenesis of NS consists in SPINK5 genetic mutation resulting in loss of functional LEKTI and ensuing excessive activation of KLK5 in the skin.

Kallikrein-Related Peptidase 5 (KLK5) plays a central role in shedding epidermis stratum corneum and inciting dermis inflammation. Active KLK5 induces stratum corneum detachment by cleavage of corneodesmosomal proteins, such as desmoglein-1, which join keratinocytes; and up-regulates inflammatory signaling by cleavage of protease-activated receptor 2 (PAR2) on keratinocytes.

Unopposed KLK5 activity results in a compromised skin barrier and an abnormal production of pro-inflammatory and pro-allergic mediators, including tumor necrosis factor (TNF), interleukin (IL)-8 and especially Th2 cytokines, such as thymic stromal lymphopoietin (TSLP) and thymus and activation-regulated chemokine (TARC). There are no approved specific therapeutic agents for the treatment of NS. Emollients are regularly used and topical keratolytic agents, glucocorticoids, and antibiotics represent the mainstay treatment. Part of the standard of care are

also oral antihistamines and retinoids. In certain severe cases, pimecrolimus and psoralen plus phototherapy are used. Despite anecdotal cases of some success, NS poorly responds to biologics that have recently shown important efficacy in the treatment of major inflammatory dermatological disorders such as psoriasis (anti-IL-17A antibodies secukinumab and ixekizumab) and atopic dermatitis (anti-IL-4R $\alpha$  antibody dupilumab). A topical Kallikrein-Related Peptidase 7 (KLK7) inhibitor (BPR277) was tested in an early phase clinical trial in NS patients and reported to have had “a treatment effect”; the plan of a late phase clinical trial was presented in 2020.

CCI

